5.10.4 Optional Interim Analyses

Given the hypothesis-generating nature of this study, the PI may choose to conduct up to two interim efficacy analyses. The interim analysis will be performed and interpreted by members of the study team.

5.10.5 Interim Safety Monitoring

For patient safety, A Bayesian toxicity monitoring rule will be implemented for the treatment related toxicity events during the duration of the treatment in all treated patients across 3 tumor groups.

The toxicity event is defined as AESIs for the combination of atezolizumab and cobimetinib may include the following:

- Non-hematologic AEs Grade ≥ 3 with the exceptions of:
- Grade 3 Nausea
- Grade ≥ 3 Diarrhea if reversible within 48 hours with maximal supportive care
- Electrolyte abnormalities that are reversible within 72 hours with supportive care and/or supplementation
- All hematologic AEs Grade ≥ 4
- Specific toxicities:
 - Grade 1–4 serous retinopathy
 - Any grade retinal vein occlusion (RVO)
 - Grade ≥ 2 cardiac disorders (e.g. atrial fibrillation, myocarditis, pericarditis and left ventricular dysfunction)
 - Rhabdomyolysis or elevated CPK
 - Grade ≥ 3 hemorrhagic event or any grade cerebral hemorrhage
 - Systemic lupus erythematosus
 - Neurological disorders: Guillain-Barré syndrome, myasthenic syndrome or myasthenia gravis, and meningoencephalitis
 - Events suggestive of hypersensitivity, cytokine release, influenza-like illness, systemic inflammatory response syndrome, or infusion-reaction syndromes
 - Ocular toxicities (e.g. uveitis, retinitis)
 - Myositis
 - Grade ≥ 3 Hepatotoxicity
 - Grade ≥ 3 rash
 - Pneumonitis

- Colitis
- Nephritis
- Endocrinopathies (diabetes mellitus, pancreatitis, adrenal insufficiency, hyperthyroidism or hypothyroidism)

Let p_{tox} be the toxicity probability, then if $\Pr [p_{\text{tox}} > 0.3] > 0.9$, we will terminate the study early. We will apply the monitoring every 5 patients. That is, we will early stop the study if we observe $[\# \text{ patients experiencing toxicity}] / [\# \text{patients being treated}] \geq 4/5, 6/10, 8/15, 9/20, 11/25, 13/30, 115/35, 16/40, 18/45, 20/50, 22/55, \text{ or } 23/60$. The operating characteristic for applying this toxicity monitoring rule is shown in Table 2.

Table 2. Operating characteristics for toxicity early stopping based 5000 simulation runs per scenario

True toxicity probability	Early stopping probability	Average sample size
0.2	0.024	58.9
0.3	0.238	51.1
0.4	0.730	32.4
0.5	0.973	18.1

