Study GP28363 is a Phase Ib, open-label, multicenter study designed to assess the safety, tolerability, and pharmacokinetics of cobimetinib plus atezolizumab in patients with advanced solid tumors. The study has two stages: Stage 1 (dose escalation) and Stage 2 (expansion). Stage 1 is designed to establish the combination MTD for cobimetinib plus atezolizumab. In Stage 2, the recommended Phase II dose and schedule were investigated in tumor-specific expansion cohorts: KRAS-mutant mCRC, NSCLC, and metastatic melanoma.

In the Stage 1 dose-escalation phase, there were no DLTs, and 60 mg cobimetinib 21/7 with 800 mg atezolizumab every 2 weeks (q2w) was determined to be the recommended Phase II dose. As of 12 October 2015, a total of 90 patients were accrued and evaluable for safety. The most common adverse events reported were diarrhea (71.1%), fatigue (55.6%), nausea (41.1%), rash (41.1%), vomiting (38.9%), decreased appetite (37.8%), constipation (35.6%), pruritis (32.2%), dermatitis acneiform (28.9%), and blood CPK increased (25.6%). The most common Grade 3 or higher adverse events reported were anemia (10.0%), diarrhea (7.8%), fatigue (7.8%), dyspnea (6.7%), rash (4.4%), and blood CPK increased (4.4%).

Nine patients experienced Grade 5 (fatal) adverse events. These included disease progression in 3 patients and large intestine perforation, asthenia, dyspnea, pneumonia, sepsis, and road traffic accident in 1 patient each. The safety of cobimetinib plus atezolizumab appeared similar to the known single-agent safety profiles of each drug; no new safety signals were noted.

In the expansion cohort for mCRC patients with KRAS-mutation (n = 23); 4 patients had a PR, 5 had SD, and 14 had progressive disease. All the patients who responded had MSI-stable tumors. Furthermore, biomarker evaluation from the serial tumor biopsy cohort showed a 4-fold increase of CD8-positive T-cell infiltration in 75% of tumors as well as increases in PD-L1 and MHC-I expression, which supports the hypothesis that this use of cobimetinib and atezolizumab has beneficial immunomodulatory effects at the tumor site that allow for immune anti-tumor activity.

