 - Includes Grade ≥ 3 elevations of CPK in conjunction with other laboratory evidence (aldolase and urine myoglobin) and clinical presentation consistent with rhabdomyolysis (such as muscle pain, signs of renal failure, dark red or brown urine) Grade ≥ 3 hemorrhage event or any grade cerebral hemorrhage

- Grade \geq 3 rash
- Grade \geq 3 Diarrhea
- Pneumonitis
- Grade \geq 3 photosensitivity (when administered with vemurafenib)
- Significant liver toxicity: AST and/or ALT $> 10 \times$ upper limit of normal
- AESIs specific to Atezolizumab:
 - Pneumonitis
 - Colitis
 - Endocrinopathies: diabetes mellitus, pancreatitis, adrenal insufficiency, hyperthyroidism and hypophysitis
 - Hepatitis, including AST or ALT $> 10 \times$ ULN
 - Systemic lupus erythematosus
 - Neurological disorders: Guillain-Barré syndrome, myasthenic syndrome or myasthenia gravis, and meningoencephalitis
 - Events suggestive of hypersensitivity, infusion related reactions, cytokine release, influenza-like illness and systemic inflammatory response syndrome.
 - Nephritis
 - Ocular toxicities (e.g. uveitis, retinitis, optic neuritis)
 - Myositis
 - Myopathies, including rhabdomyolysis
 - Grade ≥ 2 cardiac disorders (e.g. atrial fibrillation, myocarditis, pericarditis)
 - Vasculitis
 - Autoimmune hemolytic anemia
 - Severe cutaneous reactions (e.g., Stevens-Johnson syndrome, dermatitis bullous, toxic epidermal necrolysis)

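### The stopping rule's toxicity event is an open list that differs from the AESI list it is named after, and its ungraded CPK item could decide whether the trial stops

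*Combined protocol and SAP*

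**What the plan says.** Section 5.10.5 sets a Bayesian monitoring rule for treatment-related toxicity, pooled over the three tumor groups. The study ends if the posterior probability that the toxicity rate exceeds 0.3 is above 0.9. On timing: "We will apply the monitoring every 5 patients". The prior is not stated. Twelve thresholds are printed, among them "13/30, 115/35, 16/40". The operating characteristics (the second table numbered 2 in the protocol) give early stopping of 0.024, 0.238, 0.730 and 0.973 at true rates of 0.2, 0.3, 0.4 and 0.5.

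The event is introduced by "The toxicity event is defined as AESIs for the combination of atezolizumab and cobimetinib may include the following". The list has two general clauses (non-hematologic Grade ≥3 with exceptions, hematologic Grade ≥4) and a set of named toxicities. Some of these are graded (cardiac, rash, hemorrhage, serous retinopathy). "Rhabdomyolysis or elevated CPK" is not.

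Section 6.4.2.10 is the protocol's AESI list. It uses the same CPK heading but adds a sub-item on Grade ≥3 "elevations of CPK in conjunction with other laboratory evidence (aldolase and urine myoglobin") and a clinical picture of rhabdomyolysis. Its endocrine item reads "Endocrinopathies: diabetes mellitus, pancreatitis, adrenal insufficiency, hyperthyroidism and hypophysitis", whereas 5.10.5 names hypothyroidism and not hypophysitis. It also lists vasculitis, autoimmune hemolytic anemia and severe cutaneous reactions, which 5.10.5 does not name. It includes Grade ≥3 diarrhea without the exemption that 5.10.5 gives to episodes reversing within 48 hours.

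Appendix 6 (Table A3-7) continues both drugs for asymptomatic CPK elevation of Grade 1, 2 or 3. The Phase Ib summary of Study GP28363 (Section 2.7, 90 patients) gives "blood CPK increased (25.6" per cent) for any grade, and 4.4% for Grade 3 or higher.

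**The concern.** A stopping count needs a closed definition, because each patient either has an event or does not. Here the wording leaves the list open, borrows the name of a different list, and omits the grade of a laboratory finding that about a quarter of Phase Ib patients had. Because neighbouring items state their grades, a reader may well take ungraded CPK to mean any grade. Another reader may carry over the qualifier from 6.4.2.10. The two would count the same patients differently and could reach opposite decisions about ending the study. On the first reading, a finding for which Appendix 6 continues both drugs would count toward termination. The table of operating characteristics does not settle this: it is indexed by the true event rate, and the plan gives no expected rate for the event it lists.

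**Working it through.** **Inputs.** Section 5.10.5: looks at 5, 10, ..., 60 patients, with thresholds 4, 6, 8, 9, 11, 13, 15 (printed 115), 16, 18, 20, 22, 23. Section 2.7 (n = 90): CPK any grade 25.6%; Grade ≥3 CPK 4.4%, fatigue 7.8%, dyspnea 6.7%, rash 4.4%, diarrhea 7.8%. Attribution and overlap are not given. Grade ≥3 anemia (10.0%) is left out because hematologic events count only from Grade 4.

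**1. Reproducing the plan's table.** Let f_n(k) be the probability of k events at n patients without having stopped. Then f_n(k) = Σ_x f_{n−5}(k−x)·C(5,x)·p^x·(1−p)^(5−x). Mass at or above the threshold is removed at each look and added to the stopping probability. A crossing at n = 60 is not counted as early.

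| True rate | Plan: stop (mean n) | Exact: stop (mean n) |
|---|---|---|
| 0.2 | 0.024 (58.9) | 0.023 (59.0) |
| 0.3 | 0.238 (51.1) | 0.233 (51.3) |
| 0.4 | 0.730 (32.4) | 0.726 (32.9) |
| 0.5 | 0.973 (18.1) | 0.975 (18.0) |

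The table reproduces. Counting n = 60 would give 0.767 at a rate of 0.4, so the plan appears to leave that look out; the figures below do the same.

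**2. The misprinted threshold.** With a Beta(a, b) prior, the threshold is the smallest k for which Beta(a+k, b+n−k) puts more than 0.9 above 0.3. Beta(0.3, 0.7) gives all the other printed thresholds and 15 at n = 35; so does Beta(0.6, 1.4). A flat Beta(1, 1) gives 14 at n = 35, but also 3 at n = 5 and 21 at n = 55, against the printed 4 and 22. Taken literally (no stop possible at 35), stopping is 0.023, 0.232, 0.725 and 0.975, so the misprint has almost no effect on the operating characteristics.

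**3. Composite event rates, assuming independence.** Rate = 1 − Π(1 − rate_i).

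- Any-grade CPK, fatigue, dyspnea, rash: 1 − 0.744 × 0.922 × 0.933 × 0.956 = 0.388. Adding diarrhea (× 0.922): 0.436.
- Grade ≥3 CPK with the same three: 1 − 0.956 × 0.922 × 0.933 × 0.956 = 0.214. Adding diarrhea: 0.275.

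The versions without and with diarrhea bracket the exemption for episodes that reverse within 48 hours.

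**4. Early stopping if every reported event counts.**

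| CPK reading | Diarrhea | Event rate | Early stop | Mean n |
|---|---|---|---|---|
| Any grade | no | 0.388 | 67% | 35 |
| Any grade | yes | 0.436 | 86% | 26 |
| Grade ≥3 | no | 0.214 | 3% | 58.5 |
| Grade ≥3 | yes | 0.275 | 15% | 54 |

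**5. Sensitivity of the any-grade reading.** Ranges run from without to with diarrhea.

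- Full overlap (every other event in a patient who also has a CPK rise): rate 0.256, stop 10%.
- No overlap: rates 0.445 and 0.523 (simple sums), stop 89-99%.
- 80% of each rate counted as related (assumption, events independent): rates 0.319 and 0.362, stop 32-54%.
- 50% counted as related (assumption, events independent): rates 0.208 and 0.239, stop 3-6%.

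Under independence, stopping reaches 50% only if about 90% of events count as related without diarrhea, or just under 80% with it.

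**The case against.** A reader might infer that a regimen behaving as it did in Phase Ib would probably stop this trial. The documents do not support that. The rule counts treatment-related events, while Section 2.7 gives separate rates with no attribution, no overlap and no composite. The answer runs from a few per cent to nearly certain, depending on assumptions the plan does not settle. Two things push it upward: Section 6.3.2 groups events of unlikely relationship with related ones, and several ungraded items (endocrinopathies, infusion reactions, influenza-like illness) have no stated rate. Neither fixes a number.

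A reader might also think that 25.6% is close enough to the 30% limit to trip the rule by itself. At that rate the rule stops 10% of the time.

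Other points on the plan's side are fair:

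- The list differences are smaller than they look. The general clauses in 5.10.5 already capture Grade ≥3 vasculitis or hypophysitis and Grade ≥4 autoimmune hemolytic anemia; only lower grades are missed.
- The CPK heading is identical in both sections, and the qualifier in 6.4.2.10 is introduced as something included, so it is not plainly a restriction. Nor is 4.4% the rate of that qualified item, which also calls for laboratory and clinical evidence.
- The two lists serve different purposes, expedited reporting and termination, and need not be identical.
- An over-broad event errs toward stopping early, and the IND office reviews data after every five patients per group.

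These points remove the claim of probable stopping and the case for a single merged list. They do not remove the defect: the event is open, misnamed and ungraded at the item with the largest known rate. Ambiguity about the qualifier is itself a reason why the rule cannot be applied reproducibly.

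**Conclusion.** The point holds as a defect of definition. Section 5.10.5 does not fix what counts as an event, and the CPK item alone could decide whether the study continues. If all Phase Ib events are counted and taken as independent, early stopping is 67-86% under one reading and 3-15% under the other. The higher range depends on most events being judged related and on limited overlap. With any-grade CPK it drops to 10% under full overlap, 32-54% at an assumed 80% related, and 3-6% at an assumed 50%. The supportable statement is that the regimen could stop the trial under the list as written.

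The value 115/35 is impossible but nearly harmless numerically. That 15 is meant follows from the other printed thresholds under a prior such as Beta(0.3, 0.7), and is consistent with the plan's table. It does not follow from the 0.9 criterion alone, since the prior is unstated.

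**What to change.** 1. Give the stopping rule its own closed event definition with a grade for every item. Remove the open-ended verb, and do not call the event AESIs unless the list is the one in 6.4.2.10. The reporting list can stay separate.
2. Reconcile the CPK item across 5.10.5, 6.4.2.10 and Appendix 6. Copying the 6.4.2.10 qualifier into the named item is not enough, because asymptomatic Grade 3 CPK would still count through the Grade ≥3 non-hematologic clause. Which grades should count is for the investigators to decide and state.
3. State the expected treatment-related composite rate for the chosen definition, with its source or assumptions. If any-grade CPK is intended, check the 0.30 limit against that rate and add a row to the operating-characteristics table there.
4. State the prior and print 15/35.

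The cost is an amendment to wording and a short recalculation. No new patients, assessments or data are needed.

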5.10.3 Determination of Sample Size

The primary endpoint is best ORR (PR or CR), measured as per RECIST 1.1. Three parallel single-stage phase II trials will be conducted. A total of 60 patients will be enrolled, i.e., 20 patients in each tumor group. Considering the rareness of the disease, the patient accrual rate is approximately 1 to 2 patients per month per tumor group.

Sample size calculation

For each tumor group, we will estimate the best ORR and its exact confidence interval (CI). When the sample size is 20, and the response rate is 0.3, the two-sided 95% exact CI using the Clopper and Pearson method will be (0.119, 0.543).

For each tumor group, we will also compare its overall best response rate to the historical control based on the current literature. Let p represent the overall best response rate, we will perform independent Binomial test against $H_0: p=0.1$ for each group, with a 1-sided type I error rate of 0.05. The sample size of 20 will provide 76% power to detect an improved best ORR being 30% compared to 10%.

Analysis Plan

The primary outcome is the best ORR since the start of treatment. For each tumor group, we will estimate the best response rate and its 95% exact confidence interval using the Clopper and Pearson method. And we will assess the efficacy of the combination treatment by performing the independent binomial test comparing the best response rate versus the historical control for each tumor group. The primary efficacy analyses will include all treated patients who have received at least one dose of study treatment and have baseline tumor assessment. Patients who do not receive at least 1 dose of therapy will be replaced.

For each tumor group, median DOR and corresponding 2-sided 95% CI will be reported. The association between the best ORR and other variables will be assessed using the Fisher's exact test. Time-to-event outcomes, including progression free survival (PFS) and overall survival (OS), will be estimated using Kaplan-Meier method. The log-rank test will be performed to test the difference in time-to-event distributions between patient groups. Cox proportional hazards model may be utilized to include multiple covariates in the time-to-event analysis.

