Patients' demographic information (e.g. age, gender) at baseline will be analyzed, with data summarized in mean \pm standard deviation, median and range for continuous variables, and in frequency count and percentage for categorical variables. The student t-test or the Wilcoxon test may be used to compare continuous variables among different tumor patient groups. The chi-square test or the Fisher's exact test will be applied to assess the association between two categorical variables.

The safety analyses will include all treated patients who received at least one dose of study treatment. Toxicity data will be summarized by frequency tables for each tumor type group. The association between the types and severity of toxicity and the tumor group will be evaluated. No formal statistical testing will be performed on these summaries.

Summary statistics for biomarkers and their corresponding changes (or percent changes) from baseline will be tabulated by planned study day and dose in each tumor group. The time-course of biomarker measures will be investigated graphically. If there is indication of meaningful pattern over time, further analysis (eg, by linear mixed model) may be performed to characterize the relationship. Methods such as, but not limited to, logistic regression will be used to explore possible associations between biomarker measures and clinical outcomes.

MDACC Investigational New Drug (IND) office will review safety/efficacy data with Principal Investigator (and statistician if needed) at a predetermined interval as indicated next. The first analysis will occur after the first 5 subjects are treated for at least 2 cycles, per tumor group. Reports submission will continue in cohort size of 5, per tumor group, thereafter. On every report submission, the information from previous reported patients will need to be updated.

Considering the limited sample size for each tumor group, we may apply the Bayesian classification and information sharing method proposed by Lee and Chen (submitted) in the data analysis. It will provide a more efficient and more powerful way to estimate and test the response

rate for similarly performed groups. We will first cluster the tumor groups according to their response rate into the low- or high-response cluster first, and then apply the Bayesian hierarchical model to borrow information among groups within the same cluster in estimating their response rate and comparing it to the historical control.

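### Section 5.10.5: the 35-patient stopping boundary is misprinted as 115/35, and Table 2 is a best case that the toxicity rule as described does not deliver

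*Combined protocol and SAP*

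**What the plan says.** Section 5.10.5 monitors "treatment related toxicity events during the duration of the treatment in all treated patients across 3 tumor groups". The study stops if Pr(p_tox > 0.3) > 0.9; the prior is not given. On timing it says only "We will apply the monitoring every 5 patients". The count compared with each boundary is the number of patients with toxicity over the number treated. The boundaries run from 4/5 to 23/60 and include "13/30, 115/35, 16/40". Table 2 of the section is headed "Operating characteristics for toxicity early stopping based 5000 simulation runs per scenario".

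Section 5.10.3 gives the pace of enrolment: "the patient accrual rate is approximately 1 to 2 patients per month per tumor group". It also describes a review by the IND office: "The first analysis will occur after the first 5 subjects are treated for at least 2 cycles, per tumor group". That review continues in cohorts of 5 per group, and "On every report submission, the information from previous reported patients will need to be updated". Section 4.1 expects 12 months on therapy. Section 4.2 expects full enrolment at about 18 months.

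**The concern.** Table 2 is the only evidence in the plan of how fast this rule would halt a regimen that is too toxic. Events count over the whole of treatment, about 12 months, while the next five patients arrive in one to two months. Section 5.10.5 sets no minimum follow-up before a look and no pause in accrual. Because the denominator is everyone treated, a patient still under observation counts as free of toxicity until an event occurs. A rule run this way would enrol more patients before stopping than Table 2 shows. If events are not yet visible at the look, it would also stop less often. The 35-patient boundary, read literally, removes one of the looks.

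**Working it through.** **Boundaries.** At each n, take the smallest x with Pr(p > 0.3 | x, n) > 0.9 under a Beta(a, b) prior, whose posterior is Beta(a + x, b + n − x). Beta(0.3, 0.7), Beta(0.6, 1.4) and Beta(1, 2) all give 4, 6, 8, 9, 11, 13, **15**, 16, 18, 20, 22, 23. These equal the other 11 printed boundaries, with 15 at n = 35. Under Beta(0.3, 0.7) the posterior probability at n = 35 is 0.887 for x = 14 and 0.940 for x = 15. A uniform Beta(1, 1) prior does not return the printed set. On a grid of a from 0.05 to 3 and b from 0.05 to 6 in steps of 0.05, 320 priors match the 11 legible boundaries, and all 320 give 15.

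**Reproducing Table 2.** Exact binomial recursion, status complete at each look, nobody enrolled beyond it, boundary 15/35, looks at 5 to 55:

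| True rate | Table 2: stop / mean N | Recomputed | Without the 35-patient look |
|---|---|---|---|
| 0.2 | 0.024 / 58.9 | 0.0226 / 59.0 | 0.0226 / 59.0 |
| 0.3 | 0.238 / 51.1 | 0.2327 / 51.3 | 0.2317 / 51.4 |
| 0.4 | 0.730 / 32.4 | 0.7263 / 32.9 | 0.7253 / 33.1 |
| 0.5 | 0.973 / 18.1 | 0.9753 / 18.1 | 0.9751 / 18.2 |

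The agreement is within simulation error. Counting the 60-patient look as an early stop would give 0.767 at rate 0.4, so Table 2 appears to leave it out. The last column shows that the misprint hardly matters.

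**What accrual does.** Pooled accrual is 3 × (1 to 2) = 3 to 6 per month; the plan of 60 in 18 months is 3.33. Five patients arrive in 5/6 = 0.8 to 5/3 = 1.7 months. Two cycles are 56 days, or 1.84 months. During a 2-cycle wait the expected number of new patients is 3 × 1.84 = 5.5, 3.33 × 1.84 = 6.1, or 6 × 1.84 = 11.0.

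**Illustrations.** Each cell uses 20,000 simulated trials with Poisson accrual, looks to 55, and N as patients enrolled at the stop. The documents give no onset times, so those are assumptions.

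*A. 2-cycle wait at every look, accrual continues, all events within 2 cycles.* Stopping probability is unchanged. Mean N rises:

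| True rate | Table 2 | 3 per month | 3.33 per month | 6 per month |
|---|---|---|---|---|
| 0.5 | 18.1 | 23.6 | 23.9 | 28.8 |
| 0.4 | 32.4 | 36.9 | 37.2 | 40.7 |

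A hand check at rate 0.5 and 6 per month: 18.05 + 0.975 × 11.0 = 28.8.

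*B. No wait, as literally printed, onset uniform over 56 days.* At rate 0.4, stopping is 0.55 at 3 per month and 0.42 at 6 per month (Table 2: 0.730), with mean N about 44 and 50.

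*C. 2-cycle wait, accrual continues, onset averaging about 2 months* (exponential, truncated at 12 months, 60% of events within 2 cycles). At rate 0.4, stopping is 0.59 at 3.33 per month and 0.50 at 6 per month, with mean N about 45 and 51. At rate 0.5, stopping is 0.94 and 0.90 (Table 2: 0.973), with mean N about 31 and 39.

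The two conditions therefore act on different columns of Table 2. Continued enrolment raises average sample size. Incomplete status lowers stopping probability and raises sample size further.

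**The case against.** Several points on the other side stand.

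- Table 2 is computed correctly on its own terms. A reader might infer an arithmetic error in it, but the recursion reproduces it.
- The rule does have a counting convention, because its denominator is everyone treated. The fair criticism is that this convention makes the interim counts immature.
- Every loss of stopping probability rests on an assumed onset curve. The most striking of these, 0.50 in illustration C, also needs 6 patients per month, which would fill the trial in 60/6 = 10 months rather than the planned 18.
- The boundary list includes 23/60, which the illustrations leave out to match Table 2. In the 0.50 case, adding it raises eventual stopping to about 0.555, or to about 0.69 if the final count is updated to completion. It does not reduce enrolment, because all 60 are already in.
- A reader might infer that patients are left unprotected. The documents do not support that. Section 5.9 allows termination at any time for adverse events, section 5.10.3 provides a 2-cycle review with updated data, and section 6.4 puts events of special interest on the same reporting timeframe as serious events and sends them to the drug supplier within one business day.

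These safeguards do not repair the stated performance of this rule. The 5.10.3 review runs per tumor group, nothing links it to the pooled boundaries, and it does not hold enrolment. Illustration A needs no late toxicity at all, only the plan's own accrual and its only stated follow-up interval.

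**Conclusion.** The point holds in two parts. The 115/35 boundary is wrong as printed and should read 15/35; its effect is negligible, and the unstated prior is a reporting gap. Table 2 is a best case for the design as described. The sample-size shortfall is the firmer result: at a true rate of 0.5, about 24 to 29 patients against 18.1, and at 0.4, about 37 to 41 against 32.4, even when every look waits 2 cycles and all events fall within them. The fall in stopping probability has a clear direction whenever status is incomplete, but its size depends on assumed onset times and should be read as illustrative. The conclusion concerns the performance of this rule, not the trial's overall safety oversight.

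A separate minor note: the event list in section 5.10.5 has "Rhabdomyolysis or elevated CPK" without a grade, while section 6.4.2.10 expands the same item to include Grade 3 or higher elevation with supporting evidence of rhabdomyolysis. Whether other elevations count towards the boundary is left open. This has not been quantified.

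**What to change.** 1. Correct the boundary to 15/35 and state the prior.
2. Tie each pooled look to a stated follow-up, for example the 2-cycle review already in section 5.10.3, with earlier patients updated at every look. State how patients still under observation count and that accrual continues meanwhile.
3. Re-simulate Table 2 under planned accrual with a stated range of onset times, say whether the 60-patient look is included, and report the results beside the current figures.
4. Reconcile the CPK item between sections 5.10.5 and 6.4.2.10 so that one definition applies. No threshold is proposed here.

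The cost is protocol wording and one simulation, with no new patients or data. The downside is that the published operating characteristics become less favourable. Pausing accrual for 2 cycles at each of the 11 looks before 60 would restore Table 2 only if all events fall within 2 cycles. It would add up to 11 × 56 = 616 days, about 20 months, to an 18-month accrual plan. Waiting without a pause, with realistic figures shown, is the cheaper course.
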